## 1.6 Ethical Committee

All the materials have been reviewed by CEIC Hospital Clínic de Barcelona (Barcelona)

## 2 Introduction and justification

### 2.1 Background information

Infertility is an increasing global public health problem present in about 15-20% of the population of reproductive age, affecting as many as 186 million people worldwide [1]. The main cause of this increase is the age of women, but it must be highlighted that in 20% of the cases are due to an exclusive male factor, and in 30-40% of the cases a combined cause is found (male and female factor). Therefore, a male factor is present in approximately 50% of the infertile couples, a large number of them of unknown or idiopathic origin [2].

Spermatogenesis is a complex biological process that requires a highly regulated genetic and hormonal program in a singular environment created by the interaction with different cell types to orchestrate a successful differentiation process. This process occurs periodically every 72 days during a man's fertile life [3]. It has been demonstrated that semen quality is deteriorating over the time, perhaps as a result of exposition to several environmental factors related with lifestyle: drug use (such as tobacco, alcohol, marijuana, cocaine, opioids and anabolic agents), diet and overweight, disorders of the sleep-wake cycle and working conditions (continuous exposition to heat sources or toxic substances) that could impact both directly and indirectly on the complex process of spermatogenesis [4].

Currently, the impact of oxidative stress, a cellular state product of an imbalance between the generation of highly unstable molecules known as reactive oxygen species (ROS) and the antioxidant cellular capacity in male fertility is being deeply investigated [5]. High levels of oxidative stress in semen have been associated with both lower sperm concentration, sperm motility and acrosome integrity and higher sperm DNA damage and mitochondrial activity [6-10]. Moreover, it has been demonstrated the negative correlation of high levels of ROS in semen with the sperm fertilization ability and embryo quality after IVF cycles [9,11,12]. Sperm are particularly susceptible to the oxidative effects of ROS, due to the large amounts of unsaturated fatty acids in the cell membrane (lipid peroxidation). Lipid oxidation process leads to loss of membrane integrity, increased its permeability, the inactivation of cellular enzymes, structural DNA damage and cellular apoptosis.

Recent clinical trials have demonstrated the high prevalence of sperm DNA damage by up to 80% of men diagnosed with idiopathic male infertility [5-7]. This DNA damage produced during spermatogenesis or sperm maturation process could be the result of an increase of reactive oxygen species (ROS) in male reproductive tract, which are related to different known factors (chronic systemic disease, use of some drugs, radiation or pesticides, febrile processes, old age and environmental factors related to lifestyle: smoking, obesity, alcohol) and other unknown so far.

Recently, Agarwal A. et al [13], have demonstrated the usefulness of measuring oxidation-reduction potential (ORP) in semen and seminal fluid by a novel analyzer, "Mioxsys", patented by Aytu BioScience, as a diagnostic test of male fertility capacity. This allows assessing the degree of oxidative stress in the sample (assessing the balance between oxidizing and antioxidant substances), in a simple, cheap and real-time manner, which has been shown to be closely related to seminal quality; the higher ORP, the worse sperm motility.[11] Moreover, it has been

shown that the mean ORP value does not change when it is measured at different times after the collection of the sample (between 0-120 min) [13] .

## 2.2 Justification

Antioxidant supplementation has gained relevance within routine practices in patients with reproductive problems [5]. Different studies have shown the beneficial effect of antioxidant consumption against oxidative damage caused by environmental and pathological components, improving sperm characteristics associated with the seminal analysis. There are scientific evidences about the improvement of male fertility and higher rates of live newborn after antioxidant treatment in subfertile men [14].

TetraSOD® is a unique commercial product comprised of 100% lyophilized biomass of the marine microalgae *Tetraselmis chuii* strain CCFM03, which is currently marketed for food and nutraceutical applications around the world by the company Fitoplancton Marino, S.L. This microalgae product is characterized by a high content in the antioxidant enzyme superoxide dismutase (SOD), as it is produced using own (patent pending) technology developed by the company. Results of *in vitro* studies with human cell lines suggest that TetraSOD® stimulates the cellular protective mechanisms against oxidative stress, including up-regulation of genes encoding SOD, glutathione peroxidase (GPx) and catalase (CAT), as well as the nuclear factor erythroid 2-related factor 2 (NRF2) and the heme oxygenase-1 (HMOX1) inducible phase II detoxifying enzyme.

A pilot study has been previously performed in which 40 subjects were recruited and divided into two groups of 20 subjects each. In summary, the results obtained in this pilot study with the highest dose of TetraSOD® (250 mg/day) were promising, since a high statistically significant response was observed in three of the four studied parameters after three months of treatment.

Taking into account these results, a new extended double-blind randomized and placebo-controlled clinical study will be performed to confirm the positive effects of dietary supplementation with 250 mg of TetraSOD® during 3 months (corresponding to the time of a complete spermatogenic cycle) in sperm quality.

The main objective of our study is to demonstrate the usefulness and safety of TetraSOD® treatment in the improvement of sperm quality including sperm DNA fragmentation. As we mention previously, oxidative stress is one of the main causes of sperm DNA damage. Nowadays, a diagnostic test for the study of the sperm DNA fragmentation exists, but it requires a specific sperm sample processing and the results are obtained in delay-time. In our study we are going to also assess the correlation between sperm DNA fragmentation and sORP (static oxidation reduction potential) degree by the use of "Mioxsys". Therefore, the availability of a simple and cheap instantaneous response time diagnostic test seems promising for the reproductive clinics. It allows us to advance in the diagnosis of male fertility potential and in the identification of those patients susceptible to antioxidant treatment [15] in order to improve their reproductive results, increasing the chances of pregnancy both spontaneously or after assisted reproductive treatment [9,12].

A double-blind randomized placebo-controlled clinical study to verify the efficacy of TetraSOD® in the improvement of semen quality in patients with idiopathic infertility.

### 3 Objectives of the study

#### 3.1 Main objective

- To evaluate the efficacy of TetraSOD® in improving the sperm quality in patients with asthenozoospermia (low sperm motility), oligozoospermia (low sperm concentration) or oligoasthenozoospermia (low sperm concentration and motility) after 3 months of treatment.

#### 3.2 Secondary objectives

- To evaluate the improvement in the sperm oxidative stress in infertile patients after 3 months of treatment with TetraSOD®.
- To evaluate the efficacy of TetraSOD® in improving sperm DNA integrity in infertile patients.
- To establish a prognostic correlation value between sORP levels, sperm DNA fragmentation, and seminal parameters.
- To evaluate the safety of TetraSOD®.

#### 3.3 Main variables

- Seminal parameters as described in the WHO laboratory manual for the Examination and processing of human semen, Fifth Edition (manual of the WHO 2010) [16] including vitality and leukospermia.

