## 7 Statistical analysis

### 7.1 Sample size

The sample size has been calculated using the on-line tool GRANMO v7.12 (<https://www.imim.es/ofertadeserveis/software-public/granmo>). Data obtained in the previous pilot trial regarding total sperm count per ejaculate were used as a reference. With the aim to determine differences between the mean of the two experimental groups, and accepting an alpha risk of 0.01 and a beta risk of 0.2 in a two sided test, a total of 46 individuals per group are necessary to recognize as statistically significant a difference greater than or equal to  $20 \times 10^6$  spermatozoa/ml of ejaculate. The common standard deviation is assumed to be 25 (the maximum value in the previous pilot trial), with an anticipated drop-out rate of 20%. In that way, a total of 100 subjects, 50 per experimental group, will be recruited for the present clinical trial.

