### 7.2 Statistical analysis

A descriptive statistic of all the variables collected will be made.

The categorical variables will be presented in the form of lists of frequencies and proportions. For the quantitative variables, central tendency (mean and median) and dispersion (standard deviation, maximum and minimum values) will also be presented.

A double-blind randomized placebo-controlled clinical study to verify the efficacy of TetraSOD® in the improvement of semen quality in patients with idiopathic infertility.

Initial demographic and anthropometric characteristics of patients in TetraSOD® and placebo groups will be compared with independent t-test for continuous variables and chi square test for categorical ones. The non-parametric Mann-Whitney test will be applied to evaluate the effects of the dietary supplementation with TetraSOD® group vs. placebo group at the same time of study (time 0, 90 d or 180 d). Within each experimental group (TetraSOD® and placebo), the non-parametric Friedman test for matched-pairs will be applied in order to determine statistically significant differences of data recorded at the three sampling times (0, 90 d and 180 d). Significance will be accepted for  $p < 0.05$ . All analyses will be conducted with Prism 6 software.

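### No single primary variable: the whole WHO semen panel is the main variable and is tested at p < 0.05 with no success rule or multiplicity control, although the trial is sized on one variable at alpha 0.01

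*Combined protocol and SAP*

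**What the plan says.** - **Main variable (3.3).** "Seminal parameters as described in the WHO laboratory manual for the Examination and processing of human semen, Fifth Edition", "including vitality and leukospermia". No parameter is ranked first, and the panel is neither listed nor counted.
- **Main objective (3.1).** Improvement in sperm quality after 3 months of treatment, in men with low motility, low concentration or both. Sperm quality is not defined.
- **Analysis (7.2).** "The non-parametric Mann-Whitney test will be applied to evaluate the effects of the dietary supplementation with TetraSOD® group vs. placebo group", at 0, 90 and 180 d, with Friedman tests over time within each arm. "Significance will be accepted for" p < 0.05. No correction, hierarchy or success rule is given.
- **Sample size (7.1).** "Data obtained in the previous pilot trial regarding total sperm count per ejaculate were used as a reference". The calculation uses two-sided alpha 0.01, beta 0.2, SD 25 and 20% drop-out. The target difference is 20 × 10^6 spermatozoa per ml, which is a concentration, although the variable named is a total per ejaculate.
- **Justification (2.2).** The trial is meant to confirm a pilot study, and its main objective is to "demonstrate the usefulness and safety of TetraSOD® treatment in the improvement of sperm quality including sperm DNA fragmentation". Section 3.2 lists "To evaluate the efficacy of TetraSOD® in improving sperm DNA integrity in infertile patients" and safety as secondary objectives.

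**The concern.** A confirmatory trial needs a deciding test fixed in advance. Here the main variable is a panel of unstated size, each member is tested at 0.05, and nothing says whether one, several or all parameters must differ. A single significant parameter could therefore be presented as meeting the main objective, and the chance that some parameter crosses the threshold with no true effect grows with the size of the panel.

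The sample-size section does not settle the matter. It points to one variable and a stricter alpha, but 3.3 does not single out that variable and 7.2 uses a different alpha. Two analysts following the plan could reach opposite conclusions from the same data without either departing from it.

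**Working it through.** **1. Reproduce the plan's own figure.** Inputs from 7.1: difference 20, SD 25, two-sided alpha 0.01, power 0.80, drop-out 20%.

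n per group = 2 × [25 × (2.576 + 0.842) / 20]² = 36.5. Dividing by 0.8 gives 45.6, so 46, which matches 7.1. (Rounding 36.5 up to 37 first would give 47.) The plan recruits 50 per group.

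**2. Number of parameters, k (assumed).** Five is the count that can be assembled from the text: vitality and leukospermia (3.3), motility and concentration (the diagnostic definitions in 3.1) and total count (7.1). Nine is taken for a fuller panel. Neither number is stated in the documents.

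**3. Independent parameters, 90 d only.**
- Any difference at p < 0.05: 1 − 0.95^k = 22.6% (k = 5), 37.0% (k = 9).
- A difference favouring TetraSOD: 1 − 0.975^k = 11.9% (k = 5), 20.4% (k = 9).

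**4. Correlated parameters.** Test statistics were simulated as equicorrelated standard normals with no treatment effect. The correlation between parameters (ρ) is assumed. For two visits, the same parameter is assumed to correlate 0.5 between 90 and 180 d. The table gives the chance of at least one result beyond ±1.96 (any direction) or above +1.96 (favouring TetraSOD).

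| k | ρ | 90 d, any | 90 d, favourable | 90 + 180 d, any | 90 + 180 d, favourable |
|---|---|---|---|---|---|
| 5 | 0.3 | 21% | 10–11% | 35% | 18% |
| 5 | 0.5 | 18% | 9% | 31% | 16% |
| 9 | 0.3 | 33% | 17% | 52% | 27% |
| 9 | 0.5 | 27% | 13–14% | 44% | 22–23% |

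The nominal values are 5% for any direction and 2.5% for the favourable direction.

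**5. Sensitivity to stronger correlation.** At ρ = 0.7, five parameters at 90 d give 15% in either direction and 7% favourable. At ρ = 0.9 they give 10% and 5%. An assumed eight-parameter structure, with count tied closely to concentration and the motility measures tied closely to each other, gives 27% and 14%.

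**6. Not counted.** The within-arm Friedman tests are a further unadjusted route to reporting improvement. The comparison at time 0 is also left out, because it cannot show efficacy.

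**7. Does a single primary at 0.01 need more patients?** Evaluable per arm: 50 × 0.8 = 40. With standardised difference 20/25 = 0.8 and two-sided alpha 0.01, t-test power is about 82%.

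**8. Fallback of five named parameters at 0.01.** The Bonferroni bound is 5 × 0.01 = 5%. If they are independent, 1 − 0.99^5 = 4.9%.

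**The case against.** - **Section 7.1 implies the primary.** One can argue that sizing on total sperm count at alpha 0.01 makes that the primary test. This does not rescue the plan: 3.3 and 7.2 never single the variable out, 7.2 sets a different alpha, and the difference in 7.1 is not in the units of the variable it names.
- **A false claim of improvement at 20–50% instead of 5%.** A reader might infer this from the either-direction figures, and it is not supported. Those figures include differences favouring placebo. A false claim of improvement needs the favourable tail, which is about half as large and has a nominal rate of 2.5%.
- **The upper end rests on two choices.** The 44–52% range needs nine parameters, which the documents do not state, and also the 180 d visit. Section 3.1 fixes the main objective at 3 months, and 180 d follows three months off treatment (section 4), so the 90 d figures are the core case. The 180 d figures still matter, because 7.2 tests that visit at the same level without ranking it.
- **Correlation.** Count and concentration are likely to move together, which pulls the figures towards the lower end. This stands as a limit on the size. The rate stays above nominal even at ρ = 0.9.
- **Choice of variable.** Men with low motility alone are eligible, and the documents do not show that a count is the best single outcome for them. The sponsor has to justify the choice. The sizing variable is simply the only one for which the plan provides a power basis.

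**Conclusion.** The defect stands and should be fixed before analysis: a multi-parameter main variable, no single primary, no success rule, unadjusted tests at 0.05, and an alpha and variable in 7.1 that are not carried into 3.3 or 7.2.

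Confidence in the defect is high. Confidence in its size is moderate, because both panel size and correlation are assumed. With 5 to 9 parameters and ρ of 0.3 to 0.5 at 90 d, the false-positive rate is about 18–33% in either direction and about 9–17% in favour of TetraSOD, or roughly four to seven times the nominal 5% and 2.5%. Testing 180 d at the same level as well gives about 31–52% and 16–27%.

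The mismatch between 2.2 and 3.2 over DNA fragmentation and safety is a separate wording inconsistency and is not part of these error rates.

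**What to change.** 1. In 3.3 and 7.2, name one primary comparison: TetraSOD versus placebo at 90 d on the variable used for sizing in 7.1. First reconcile its unit (total per ejaculate or per ml), and recheck the difference and SD in that unit.
2. State one alpha in both 7.1 and 7.2. If 0.01 is kept, the figures in 7.1 give about 82% t-test power with 40 evaluable per arm, so no extra patients are needed. That holds only if the difference of 20 and the SD of 25 survive the unit check.
3. Make the other semen parameters at 90 d secondary with Holm adjustment, and list them by name. Make 180 d a secondary persistence analysis.
4. If the sponsor prefers several main parameters, name at most five at 90 d and test each at 0.01, which keeps the family error at or below 5%.
5. Separately, align 2.2 with 3.1 and 3.2 on the status of DNA fragmentation and safety.

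The cost is protocol and SAP wording only. The sponsor gives up the freedom to claim success on whichever parameter turns out significant.

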#### 3.4 Secondary variables

- Sociodemographic variables.
- Evaluation of the degree of sperm DNA fragmentation in semen samples using the COMET assay.
- Evaluation of sORP by Mioxsys.
- Sperm ROS intracellular and sperm DNA oxidation.
- Adverse events attributable to the treatment or study recommendations.

### 4 Study Design

Monocentric, prospective, randomized, double-blind and placebo-controlled clinical study to evaluate clinical parameters, seminal quality, oxidative stress and DNA fragmentation, in astheno/oligozoospermic patients attending to the Andrology unit of the “Hospital Clínic de Barcelona”.

They will be randomized into two groups: experimental group (TSOD food supplement) and control group (Placebo). The experimental group will receive a daily dose of 250 mg of TetraSOD® during three months and the control group will receive a daily dose of placebo during the same period of time. After three months of treatment, both groups will stop using TetraSOD® or placebo and a wash-out period of 3 months will start.

The intervention group will be assigned to each patient according to the assigned code in order of inclusion to the study and that will serve for the randomization of the patients. The code lists will be previously prepared through an informatic program. The ratio of experimental and control group will be 1:1. The randomization numbers will be distributed by blocks. The study is designed to make the assignment double-blind; therefore, the randomization sequence will be hidden and only visible by the study monitor.

The Placebo and TetraSOD® capsules will be prepared in such a way that they are indistinguishable from each other. The participants in the study, as well as the technicians in contact with the patients, in charge of preparing questionnaires, distributing capsules, taking samples, etc., will not be able to know which capsules correspond to each experimental group.

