### 5.1 Inclusion criteria

- Age: 18 to 45
- Male patients with idiopathic infertility classified with asthenozoospermia, oligozoospermia or oligoasthenozoospermia after seminal assessment.
- Not achieving pregnancy after at least one year of intercourse with the same partner without protective measures

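### Semen phenotype at entry is used neither in allocation nor in the arm comparisons, which costs precision and could dilute the effect if benefit is confined to men with the deficit

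*Combined protocol and SAP*

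**What the plan says.** Section 3.1 sets one efficacy objective, better sperm quality in men with "asthenozoospermia (low sperm motility), oligozoospermia (low sperm concentration) or oligoasthenozoospermia (low sperm concentration and motility) after 3 months of treatment". Section 5.1 admits the same three types: "Male patients with idiopathic infertility classified with asthenozoospermia, oligozoospermia or oligoasthenozoospermia after seminal assessment". Neither section gives a quota or an expected share for any type.

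The main variables in section 3.3 are "Seminal parameters as described in the WHO laboratory manual for the Examination and processing of human semen". No single parameter is primary, and none is tied to a phenotype.

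On allocation, section 4 says "The intervention group will be assigned to each patient according to the assigned code in order of inclusion to the study", and then "The ratio of experimental and control group will be 1:1. The randomization numbers will be distributed by blocks". Block size and stratification factors are not mentioned.

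Section 7.1 sizes the trial on one variable: "Data obtained in the previous pilot trial regarding total sperm count per ejaculate were used as a reference". The target difference is 20 × 10^6 per ml, with SD 25, two-sided alpha 0.01, 80% power and 20% drop-out. This gives 46 per group, and 50 are to be recruited.

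On analysis, section 7.2 says "The non-parametric Mann-Whitney test will be applied to evaluate the effects of the dietary supplementation with TetraSOD® group vs. placebo group", at 0, 90 and 180 days, with significance at p < 0.05. It plans no phenotype subgroup, stratum, covariate or adjustment for baseline.

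**The concern.** The three patient types are defined by concentration and motility, which are also outcomes. Phenotype is therefore a strong predictor of where a man's concentration and motility will lie, whichever arm he is in. The plan makes no use of it.

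Three things follow, and they differ in how firmly they stand.

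- **Precision.** Differences in level between phenotypes stay in the error term of every comparison of concentration or motility. A chance difference in phenotype mix between arms is not corrected by anything in section 7.2.
- **Interpretation.** The objective names three patient types. A whole-arm difference does not show which of them improved, or whether an abnormal value was corrected.
- **Possible dilution.** Some men will be compared on a parameter that was not their deficit at entry. If the product helps only where there is a deficit, those men add variability and no effect.

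**Working it through.** **1. The plan's own figure.** Inputs from section 7.1: difference 20, SD 25, alpha 0.01 two-sided, power 0.80, drop-out 20%.

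n = 2 × [25 × (2.576 + 0.842) / 20]² = 36.5 per group; 36.5 / 0.80 = 45.6, so 46. The stated figure reproduces, and the arithmetic is not at fault. With 50 recruited and 20% lost, 40 per arm remain.

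**2. Precision, with the same effect in every man.** Assumptions not in the documents: SD 25 within phenotype, a gap of D = 30 units between phenotype means, and a share f of men with low motility only of 20, 33 or 50%.

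Unstratified SD = √(25² + f(1−f) × 30²), which gives 27.7, 28.7 and 29.2. Power = Φ(20 / (SD × √(2/40)) − z).

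| f | alpha 0.01 | alpha 0.05 |
|---|---|---|
| no gap (D = 0) | 84% | 95% |
| 20% | 74% | 90% |
| 33% | 71% | 88% |
| 50% | 69% | 87% |

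Removing the between-phenotype variance moves power back towards the first row. A simulation of the rank tests themselves (40 per arm, alpha 0.05, uniform effect of 20, gap of 30) put the unstratified test at about 84–88% and van Elteren at 92–93%. With no gap, van Elteren cost under 1 point.

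**3. Chance imbalance.** With 50 per arm, the SD of the between-arm difference in phenotype share is √(2f(1−f)/50), or 8 to 10 percentage points. A difference of 10 points or more then has a chance of about 21–32% (normal approximation; exact counts can be somewhat higher). A difference of 20 points or more has a chance of about 2–7% (exact, ignoring blocks). With a gap of 30, the resulting shift in the arm difference has an SD of 2.4 to 3.0 units, against a standard error of 25 × √(2/40) = 5.6. This is the same variance as in step 2 seen from another side, not an extra loss.

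**4. Dilution, if the gain of 20 occurs only in low-concentration men.** Pooled difference = 20 × (1−f), SD held at 25, standard error 5.59.

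| f | pooled difference | difference / SE | power, alpha 0.01 | power, alpha 0.05 |
|---|---|---|---|---|
| 0 | 20 | 3.58 | 84% | 95% |
| 20% | 16 | 2.86 | 61% | 82% |
| 33% | 13.4 | 2.40 | 43% | 67% |
| 50% | 10 | 1.79 | 22% | 43% |

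Both alphas are shown because section 7.1 sizes at 0.01 and section 7.2 tests at 0.05. Allowing for the extra spread that a mixed response creates in the treated arm takes a further 2 to 3 points off the alpha 0.05 column.

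**5. Restricting to men with the deficit, under the same assumption.** With 40 × (1−f) men per arm and a difference of 20, power is 73, 64 and 48% at alpha 0.01, and 89, 83 and 72% at alpha 0.05. This beats the pooled comparison in each scenario, but at alpha 0.01 all three values are below the planned 80%.

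**The case against.** Section 2.1 links oxidative stress to lower concentration, lower motility and DNA damage alike. Pooling men with idiopathic infertility under one antioxidant rationale is therefore a defensible choice, and nothing in the documents says that benefit is limited to men with a deficit. This stands, and it makes dilution a possibility only.

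The sizing figures may already be pooled. Section 7.1 draws on a pilot whose phenotype mix is not described. If that mix was similar, a difference of 20 anchored to the pilot needs no (1−f) multiplier, and an SD of 25 may already contain the between-phenotype spread. This stands too. Step 4 then shows no loss, and step 2 starts from too large a within-phenotype SD.

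A reader might infer that the allocation method itself causes dilution or bias. It does neither. Unstratified blocked allocation is valid, and phenotype imbalance is part of ordinary sampling error. Dilution would come from broad eligibility combined with a pooled analysis, so separate block lists alone would not cure it. The absence of stratification is also read from silence, since section 4 names no factor but does not rule one out.

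A reader might also infer that the sizing variable is normal in every man with low motility only. Section 3.1 defines the types by concentration, whereas the section 7.1 reference is total count per ejaculate, which also depends on volume. A normal concentration does not guarantee a normal total count.

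Finally, deficit-specific comparisons add tests to a plan that has no single primary parameter and no multiplicity rule. That is a fair limit on the remedy: they should be supportive only.

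None of this answers the precision point. A predictor known at entry goes unused, and using it costs almost nothing.

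**Conclusion.** The point holds as one of lost precision and limited interpretability, with dilution as a conditional risk. Phenotype is known at entry and closely tied to the main variables, yet sections 4 and 7.2 do not use it.

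With a uniform effect of 20, 40 men per arm, alpha 0.05 and an assumed 30-unit gap between phenotypes, stratifying the rank test raises power from about 84–88% to 92–93%. If the gain is confined to low-concentration men, and 20 is the effect in those men, pooled power at f = 20, 33 and 50% is 61, 43 and 22% (alpha 0.01) or 82, 67 and 43% (alpha 0.05). If the pilot's 20 was already a pooled effect, nothing is lost to dilution.

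The stronger reading, that many men are affected and that the effect is diluted, is not supported. No phenotype shares are given for the trial or the pilot, and at alpha 0.05 with 20% of men having low motility only, power is still just above 80%. The phenotype shares, the 30-unit gap and the restriction of benefit are all assumptions.

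**What to change.** 1. **Section 4.** If randomisation has not started, prepare the computer-generated block lists separately for two strata: low concentration (oligo- or oligoasthenozoospermia) and low motility only (asthenozoospermia). Define the strata from the seminal assessment that qualified the man for entry.
2. **Section 7.2.** Make the 90-day arm comparison a van Elteren test stratified by that factor, and keep it as the main all-patient analysis. This applies even if randomisation has begun, provided it is written in before unblinding.
3. **Section 7.2.** Prespecify two sets of 90-day comparisons as supportive, not as further confirmatory tests: count and concentration in men with low concentration at entry, and motility in men with low motility at entry. Report results by phenotype when interpreting the section 3.1 objective.

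Stating the pilot's phenotype mix and the mix expected here would let a reader judge whether the 20 × 10^6 per ml is already a pooled figure.

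**Cost.** Two code lists instead of one and a few lines in section 7.2, with no extra patients, visits or assays. If phenotype turns out not to be prognostic, the stratified test loses under 1 point of power. The supportive comparisons use fewer men and are less precise, most noticeably if the product works equally in everyone.
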